#### 4.1.3 Selection of doses in the trial

For the concomitant radiochemotherapy phase, the chosen starting dose of BIBW 2992 in this study is 20 mg, which has been a tolerable dose when combining BIBW 2992 with different types of chemotherapy (U03-3218). In the current trial, BIBW 2992 dose escalation will stop at a maximum dose of 40 mg daily (section 4.1.4.1.1), which is an effective dose for BIBW 2992 monotherapy for continuous dosing (U03-3218).

For the maintenance phase, 40 mg daily in both treatment regimens will be administered. Data from trial 1200.36 indicate that 40mg of BIBW 2992 in combination with TMZ is well tolerated.

The dose schedule in Regimen U and M are described in figure 4.1.3: 1 and 4.1.3: 2 respectively

[figure not shown]

Figure 4.1.3: 1 Dosing schedule Regimen U (Unmethylated MGMT)

[figure not shown]

Figure 4.1.3: 2 Dosing schedule Regimen M (Methylated MGMT or Unmethylated MGMT after determination of regimen U MTD)

#### **4.1.4 Selection and timing of doses for each patient**

##### **4.1.4.1 BIBW2992 (Regimen M and U)**

During RT: patients will take a single oral dose of BIBW 2992 from Day 1 to Day 42 (section 4.1.4.1.1).

During maintenance phase:

Regimen M: patients will take a daily single oral dose of BIBW 2992 (40 mg):

- in combination with TMZ up to end of cycle 6
- followed by BIBW2992 monotherapy until either progression or undue side effect, whichever occurs first.

Regimen U: patients will take a single oral dose of BIBW2992 monotherapy (40 mg) daily until either progression or undue side effect, whichever occurs first.

Dose escalation is prohibited in any situation other than described in section 4.1.4.1.1

BIBW 2992 should be taken at the same time each day ( $\pm$  2 hours) in the morning at least one hour before food intake. Food is not allowed for at least 1 hour after dose administration due to an observed food effect with BIBW 2992. The tablet should be swallowed with a glass of water (~250 mL). BIBW 2992 tablets are film-coated and therefore should not be chewed or crushed.

If patients can not swallow tablets (e.g G-Tube) BIBW 2992 can be dispersed according to the following procedure:

- Place the tablet into a glass containing 50 mL isotonic sodium chloride solution.
- Stir until the tablet is broken up into very fine particles (about 15 minutes).
- Drink the suspension immediately or administer via a gastric tube.
- Rinse the glass with another 50 ml of isotonic sodium chloride solution and drink or administer the supplementary solution via the gastric-tube again (to pick up any drug remaining in the glass/gastric-tube).

Pharmacokinetic sampling will be performed on Day 8, 15 and 29 of concomitant RT treatment (PK-visits days). On these days patients should not take the trial medication at home and should not eat prior to their visit to the study site.

Missed doses of BIBW 2992 can be made up if taken within 3 hours of the regularly scheduled time. Otherwise, the dose should be skipped and subjects should take the next scheduled dose at the usual time. Patients with emesis should not take a replacement dose.

##### **4.1.4.1.1 Dose escalation scheme for BIBW**

Initially, 3 evaluable patients will be treated per dose level. As soon as one patient experiences a DLT (see section 5.2.3), 3 new patients will be treated at that dose level, to treat a minimum of 6 evaluable patients. If no other patients experience DLT the dose will be escalated to the next level and 3 further patients treated. If two or more of six patients

experience DLT, three additional patients will be treated at one dose tier below unless six have already been treated at that dose tier.

The MTD (see section 5.2.4) is the highest dose at which no more than one of 6 patients experiences DLT. Once the MTD is determined, patient enrolment at higher dose tiers will be suspended.

The MTD cohort in each Regimen may be expanded to include up to 12 patients.

Intra-patient dose escalation will not be permitted.

The first three patients at each dose level will be treated and observed for at least 6 weeks (42 days) during RT before the next cohort of new patients are treated at the next higher dose level (Table 4.1.4.1.1: 2 and 4.1.4.1.1: 3).

Table 4.1.4.1.1: 1 Rules for dose escalation for regimen M and U

Number of Patients with DLT at a Given Dose Level	Escalation Decision Rule
0 out of 3	Enter 3 patients at the next dose level.
1 out of 3	Enter at least 3 more patients at this dose level. - If 0 of these 3 patients experience DLT, proceed to the next dose level. - If 1 or more of this group suffer DLT, then dose escalation is stopped. Three (3) additional patients will be entered at the next lower dose level if only 3 patients were treated previously at that dose.
$\geq 2$ out of 3	Dose escalation will be stopped. Three (3) additional patients will be entered at the next lower dose level if only 3 patients were treated previously at that dose.

The decision regarding dose escalation steps will only be made after agreement with the sponsor's Trial Clinical Monitor (TCM).

Dose escalation and entry of patients into the next dose cohort will begin only after accrual of the required minimum number of patients has been achieved and all patients in the cohort are considered following completion of 6 weeks BIBW2992 treatment ((42 days ) during RT). Patients who are not treated until the end of these 6 weeks for any reasons other than DLT will be replaced (section 6.3.1).

If for any reasons other than DLT the schedule of radiotherapy need to be changed (e.g. bank holidays..), missed treatment fractions should be compensated for by additional treatment fractions delivered beyond 42 days to a total of 60Gy). The DLTs will be assessed until the patients finish their RT treatment (60Gy).

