#### 4.1.2 Method of assigning patients to treatment groups

Patients meeting all the inclusion and none of the exclusion criteria can be entered if they have provided written informed consent and if the dose cohort corresponding to their methylation MGMT status is not filled.

Patients with a methylated (or unmethylated after determination of regimen U MTD) MGMT promoter will be assigned to regimen M and patients with an unmethylated MGMT promoter will be assigned to regimen U.

All patients will receive treatment with BIBW 2992 and RT (regimen U) or TMZ, BIBW 2992 and RT (regimen M) as described in Section 4.1.4

BIBW 2992 dose will be escalated in cohorts of three in absence of DLT (Section 5.2.3 and 5.2.4)

In each regimen, treatment slots will be assigned by the sponsor's Trial Clinical Monitor (TCM) in close communication (email/phone) with the recruiting sites. Recruitment will be based on a competitive basis between sites.

Note: If participating sites identify two patients for a cohort at the same time, both patients may be entered into that dose cohort, resulting in more than three patients in that dose cohort.

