## Regimen U

Three patients will start at dose level U1. Dose escalation will proceed in each subsequent cohort according to the following scheme.

Table 4.1.4.1.1: 2 Treatment Schedule Regimen U

	Cohort	BIBW 2992
Regimen	Dose Cohort	mg/day
U	Cohort U1	20
U	Cohort U2b	30 *
U	Cohort U2	40

\*An intermediate dose cohort of BIBW 2992 at 30 mg may be explored if 40 mg is not tolerated (more than two patients with DLT).

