### 5.2.4 Maximum Tolerated Dose (MTD)

7. The MTD is defined as:
8. The dose of BIBW 2992 when given concomitantly with TMZ and RT (Regimen M) or BIBW 2992 when given concomitantly with radiotherapy (Regimen U) which is one dose tier below that dose at which two or more out of six patients experienced drug-related DLTs during the 6 weeks (42-day) RT treatment period. DLT experienced after the start of the maintenance treatment period will be examined separately. At the MTD, no more than one patient out of six patients may experience DLT, i.e., MTD is defined as the

highest dose studied for which the incidence of DLT is no more than 17% (i.e. 1/6 patients).

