## **7.6 DETERMINATION OF SAMPLE SIZE**

Forty eight patients will be required; if for each of the study treatment regimens (Regimen M and Regimen U), the MTD cohort is expanded to include 12 patients and the other two dose cohorts require 6 patients each.

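### Section 4.1.4.1.1 states the back-fill rule for the tier below a failed dose in two incompatible ways, and the table version can leave the candidate MTD tier short of the six patients on which the MTD is defined

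*Protocol*

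**What the plan says.** Protocol Section 4.1.4.1.1 gives the rule for completing the tier below a failed dose twice.

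- **Prose:** after two or more DLTs in six, "three additional patients will be treated at one dose tier below unless six have already been treated at that dose tier".
- **Table 4.1.4.1.1: 1, both stopping rows:** "Three (3) additional patients will be entered at the next lower dose level if only 3 patients were treated previously at that dose".

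Other provisions decide whether the difference matters:

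- Section 4.1.2, on two patients identified at the same time: "both patients may be entered into that dose cohort, resulting in more than three patients in that dose cohort".
- Section 5.2.4: "At the MTD, no more than one patient out of six patients may experience DLT". Section 4.1.4.1.1 defines the MTD on the same one-in-six basis.
- Section 4.1.4.1.1, on expanding a cohort after one DLT: "3 new patients will be treated at that dose level, to treat a minimum of 6 evaluable patients". On non-completers: "Patients who are not treated until the end of these 6 weeks for any reasons other than DLT will be replaced".
- Footnotes to Tables 4.1.4.1.1: 2 and 4.1.4.1.1: 3: the intermediate 30 mg cohort "may be explored if 40 mg is not tolerated (more than two patients with DLT".
- Section 7.6 counts patients on the basis that "the MTD cohort is expanded to include 12 patients and the other two dose cohorts require 6 patients each".

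The SAP adds no rule. Its Section 7.4 refers back to Protocol Section 5.2.4 for the MTD. Its Section 6.3 defines only a treated set, with no set of DLT-evaluable patients.

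**The concern.** The two wordings have different triggers, and nothing says which prevails. The prose fills any lower tier that has fewer than six; the table fills it only if it has exactly three. Section 4.1.2 makes a tier of four a permitted outcome under competitive recruitment across sites, so the gap can arise without any protocol violation.

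The unit of counting adds a second route. Cohorts are opened and expanded in evaluable patients, but both back-fill clauses count treated patients. One non-DLT replacement gives four treated and three evaluable, and the table read literally then adds nobody.

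At stake is the primary endpoint. Following the table can leave the dose about to be named the MTD with three or four evaluable patients, which does not satisfy the protocol's own definition.

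A smaller gap sits beside this one. The prose expands to six after one DLT and stops on two or more of six, but gives no exit for two DLTs in the first three. The table stops there, which is the sensible reading, and the prose should agree with it.

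**Working it through.** **1. The plan's own figure.** Section 7.6: 2 regimens × (12 + 6 + 6) = 48, as stated. That is 24 per regimen, against up to 30 allowed in Section 3.3, so there is room for 30 − 24 = 6.

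**2. Each rule applied literally to the lower tier.**

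| Treated before back-fill | After prose rule | After table rule |
|---|---|---|
| 3 | 6 | 6 |
| 4 | 7 | 4 |
| 5 | 8 | 5 |
| 6 | 6 | 6 |
| 7 | 7 | 7 |

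The rules agree at three and at six or more. They conflict at four and five, where the table leaves the tier below six.

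**3. Replacement.** With four treated and three evaluable, the prose adds three (six evaluable) and the table adds none (three evaluable). If each patient has probability q of non-DLT replacement, the chance that at least one of the first three is replaced is 1 − (1 − q)³. The documents give no q. At an assumed 10% this is 27%; at 5% it is 14% and at 20% it is 49%.

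**4. Does the 30 mg cohort take over?** The footnote opens it on more than two DLTs at 40 mg. With exactly two, 40 mg has already failed and the tier to complete is 20 mg. Let p be the true DLT rate at 40 mg, which the documents do not give. Under the table:

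- Stop with exactly two DLTs = P(2 of 3) + P(1 of 3)².
- Stop with three or more = P(3 of 3) + P(1 of 3) × P(≥2 of 3).

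| Assumed p | Exactly two | Three or more | Share with exactly two |
|---|---|---|---|
| 20% | 0.244 | 0.048 | 84% |
| 1/3 | 0.420 | 0.152 | 73% |
| 50% | 0.516 | 0.313 | 62% |

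**5. Chance that the lower tier is accepted.** Here p is the true DLT rate at the lower tier, again assumed. The tier escalated with no DLT and is accepted if it ends with at most one.

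- Four evaluable, no top-up: (1 − p)⁴. Filled to six: (1 − p)⁴ × P(≤1 of 2). Filled to seven, as the prose does: (1 − p)⁴ × P(≤1 of 3).
- Three evaluable, no top-up: (1 − p)³. Filled to six: (1 − p)³ × P(≤1 of 3).

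| Assumed p | 4, no top-up | 4 to 6 | 4 to 7 (prose) | 3, no top-up | 3 to 6 |
|---|---|---|---|---|---|
| 20% | 41% | 39% | 37% | 51% | 46% |
| 1/3 | 20% | 18% | 15% | 30% | 22% |
| 50% | 6% | 5% | 3% | 13% | 6% |

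Worked at p = 1/3: (2/3)⁴ = 0.198; × (1 − 1/9) = 0.176; × 20/27 = 0.146. For three: (2/3)³ = 0.296; × 20/27 = 0.219.

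**6. Precision.** With no DLT in n patients, the one-sided exact 95% upper limit is 1 − 0.05^(1/n): 63% for n = 3, 53% for n = 4, 39% for n = 6.

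**The case against.** The strongest reply is that the conflict is narrow and the protocol corrects itself. The rules agree for the planned cohort of three. A tier of four with one DLT would be expanded anyway, so what remains is mainly a clean 0/4 at the tier below a failed dose. A tier of four does not meet the MTD definition, so no MTD could properly be declared there. Reading the table's condition as meaning not yet expanded to six reconciles everything. The sponsor's Trial Clinical Monitor must agree escalation decisions, and the planning basis of 12 at the MTD points away from stopping at four. The narrowness stands. The rest does not settle the text: agreement by the monitor is an approval step, expansion to 12 is optional and presupposes that an MTD has been identified, and the reconciling reading is exactly what the protocol should say.

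It can also be said that a cohort described in evaluable patients should be counted that way throughout, so a replaced patient does not make it four. That is the natural intention, and the prose handles the one-replacement case correctly. The literal problem there lies with the table.

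The synopsis describes 30 mg as the de-escalation step if 40 mg is not tolerated, without the footnote's threshold. If that wording governs, 30 mg could open after two DLTs. This would postpone the question about 20 mg rather than answer it. The 62% to 84% shares in step 4 depend on the footnote; the contradiction between prose and table does not.

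Finally, for a tier of four the acceptance probabilities move by only one to two points when it is filled to six, and by three to five when it is filled to seven. That is correct.

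**Conclusion.** The concern holds. The same decision rule on the primary endpoint is written twice with different results at lower tiers of four or five, and the protocol itself permits such tiers. Following the table leaves the candidate MTD tier below six. This conclusion comes from the text and needs no assumed rate.

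The size does depend on assumptions. Over true DLT rates of 20% to 50%, the missing top-up to six changes the chance of accepting the tier little when four patients are evaluable, and by about 5 to 8 percentage points when only three are. The clearer loss is information: an upper limit of 53% or 63% for the DLT rate, where six clean patients would give 39%. The point should be fixed because it bears on the MTD and wording alone resolves it, even though the circumstances that trigger it are limited.

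**What to change.** In both stopping rows of Table 4.1.4.1.1: 1, replace the condition for back-filling with: *if fewer than 6 evaluable patients were treated at that dose, enter enough to reach at least 6*. Use the same sentence in the prose in place of its present exception for six treated patients. Add to the prose: *during escalation, before any expansion to 12, two or more DLTs at a dose, whatever the cohort size, stop further entry at that dose.*

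The change is confined to wording in Section 4.1.4.1.1. It costs two more patients for a lower tier of four evaluable, or the usual three if one of the four was replaced. Section 7.6 already counts at least six in every cohort, and the 24 planned per regimen are within the 30 allowed, so the sample size need not increase. The 30 mg footnote threshold is a separate inconsistency, and this fix works whichever way it is resolved.

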## FLOW CHART –REGIMEN U: UNMETHYLATED MGMT PROMOTER

Study Periods	Screening Period		Concomitant Treatment Period (Day 1-42)					C 1 & onward 	End of Treatment	Follow-up
	SV1	SV2	RT1	RT2	RT3	RT4	RT5	CxV1 a	EOT 	FU 
Visit abbreviation	SV1	SV2	RT1	RT2	RT3	RT4	RT5	CxV1a	EOT	FU
Day	-35 to -1		1	8	15	29	42	+d28		
Informed Consent 	X	X								
In-/Exclusion Criteria		X								
MGMT test result		X								
Cerebral MRI		X 						X 	X 	
Demographics	X	X 								
Urine or Serum β-HCG (females) 		X							X	
Medical History		X								
Echo or MUGA 		X							X	
Physical Examination 		X			X		X	X	X	
12 Lead Digital ECG		X		X				X 	X	
MMSE			X					X 	X	
Karnofsky performance score		X					X	X	X	X
Concomitant Therapy		X	X	X	X	X	X	X	X	X
Vital Signs		X	X	X	X	X	X	X	X	
Safety lab 		X	X	X	X	X	X	X	X	X
Adverse Events			X	X	X	X	X	X	X	X 
Compliance check				X	X	X	X	X	X	
Blood samples for PK 				X	X	X				
Dispense study medications			X			X	X	X		
Radiotherapy 			2 Gy once daily five days per week, total dose 60 Gy							
BIBW 2992 administration			Continuous oral once daily 							
Termination of study medication									X	

a x is the number of treatment (cycle)

 Written informed consent must be obtained before any study specific procedures are performed. This is a 2 steps consent. Informed consent number 1 must include consent to collection of demographic data and consent to send tumour sample from surgery to central laboratory for MGMT status assessment. If MGMT status already available (see section 5.6.1.1), patients will not need to sign Informed consent number 1 but only Informed consent number 2. Informed consent number 2 will be obtained for patients who have their MGMT test status result available and must include consent to all study procedures.

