### 1.2.2 Temozolomide

Temozolomide (TMZ) is an orally administered, second generation imidazotetrazine prodrug with essentially 100% oral bioavailability. TMZ spontaneously converts to the active alkylating agent 5-(3-methyltriazene-1-yl) imidazole-4-carboximide (MTIC) with extensive tissue distribution, including penetration of the blood-brain barrier and the cerebrospinal fluid. TMZ has notable antitumour activity against recurrent GBM (R08-1057), recurrent anaplastic astrocytoma, and advanced malignant melanoma, and other refractory cancers. TMZ has shown activity when added to radiotherapy for treatment of newly diagnosed GBM (R08-1056).

TMZ is rapidly absorbed and spontaneously converts to the active metabolite MTIC. Maximum plasma concentrations are observed 30 to 90 minutes after oral intake, and the plasma half-life is approximately 2 hours, with some delayed absorption when taken with food. Pharmacokinetics in the CSF compared with plasma showed an AUC of approximately 20% of the AUC. Patients usually tolerate TMZ well; mild to moderate adverse effects are nausea and vomiting that are usually easily controlled with standard antiemetic drugs, constipation, and some fatigue. The most serious and dose-limiting toxicity, observed in less than 10% of patients, is noncumulative myelosuppression, particularly thrombocytopenia occurring 3 to 4 weeks after treatment start,

TMZ is indicated for the treatment of patients with newly diagnosed glioblastoma multiforme concomitantly with radiotherapy and subsequently as monotherapy treatment. TMZ is also

indicated for treatment of malignant glioma, showing recurrence or progression after standard therapy. In the concomitant phase TMZ is administered orally at a dose of 75 mg/m^2 daily for 42 days concomitant with focal radiotherapy (60 Gy administered in 30 fractions) without dose reductions, but delay or discontinuation of TMZ can be considered weekly according to haematological and non-haematological side effect criteria. The TMZ is usually continued throughout the 42 day concomitant period (up to 49 days) in absence of adverse reaction.

Four weeks after completing the TMZ + Radiotherapy phase, TMZ is administered for up to 6 cycles of monotherapy treatment. The dose in cycle 1 (monotherapy) is 150 mg/m^2 once daily for 5 days followed by 23 days without treatment. At the start of Cycle 2, the dose is escalated to 200 mg/m^2 in absence of side effects.

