5. ENDPOINTS

5.1 PRIMARY ENDPOINTS

Investigator defined dose limiting toxicity during concomitant treatment period:

At least one AE meeting the criteria for dose limiting toxicity (DLT; as determined by the investigator and defined in Section 5.2.3 of the CTP) with onset during the 42 day concomitant treatment period when trial medication is given concomitantly with radiotherapy (RT).

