7.4 PRIMARY ENDPOINTS

DLT during concomitant treatment period:

The analysis of the primary endpoint will summarise DLT using descriptive statistics with the aim of determining the maximum tolerated dose (defined in Section 5.2.4 of the CTP) of:

- Afatinib in combination with TMZ when given concomitantly with RT (Regimen M);
- Afatinib when given concomitantly with RT (Regimen U).

An overall summary of AE occurrences with onset during the concomitant treatment period, which were defined to be DLTs by the investigator, will be presented. This will include the following AE attributes:

- Preferred term,
- Maximum CTCAE grade,
- Outcome,
- Time to first occurrence (relative to start of trial medication; see [Section 9.2](#) of this document).

Any AE meeting the criteria for DLT, regardless of date of onset, will be considered a significant adverse event (SIAE). The analysis of non-serious SIAEs and serious adverse events (SAEs) is described in [Section 7.8.1](#) of this document.

DLTs with onset after the concomitant treatment period will be listed separately.

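### Protocol 4.1.4.1.1 assesses DLTs until 60 Gy is complete, but SAP 5.1 limits the primary endpoint to a 42-day period, so a DLT during a radiotherapy overrun has no single counting rule (minor)

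*Protocol*

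**What the plan says.** **Escalation rule.** Protocol 4.1.4.1.1 covers radiotherapy that slips for reasons other than DLT, with bank holidays as its example: "missed treatment fractions should be compensated for by additional treatment fractions delivered beyond 42 days". It then sets the assessment period: "The DLTs will be assessed until the patients finish their RT treatment (60Gy". On timing, the first three patients at each level are to be "treated and observed for at least 6 weeks (42 days) during RT before the next cohort". Escalation also needs the agreement of the Trial Clinical Monitor.

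**MTD definition.** Protocol 5.2.4 places the MTD one tier below the dose at which "two or more out of six patients experienced drug-related DLTs during the 6 weeks (42-day) RT treatment period". It goes on to set aside, for separate examination, DLTs that occur once maintenance has begun. At the MTD no more than 1 of 6 patients (17%) may have a DLT.

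**Primary endpoint.** SAP 5.1 requires a DLT "with onset during the 42 day concomitant treatment period when trial medication is given concomitantly with radiotherapy (RT". SAP 7.4 takes the MTD definition from Protocol 5.2.4 and adds: "DLTs with onset after the concomitant treatment period will be listed separately". The Regimen U flow chart heads the period "Concomitant Treatment Period (Day 1-42".

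**Dose.** Protocol 4.1.4.1 gives BIBW 2992 during radiotherapy from Day 1 to Day 42, and 40 mg daily in maintenance.

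**The concern.** The rule that extends DLT assessment past Day 42 stands only in the dose-escalation section. The SAP's primary endpoint carries a 42-day period and does not mention an overrun, and for the MTD the SAP points to 5.2.4, not to 4.1.4.1.1. A DLT after Day 42 but before the last fraction therefore counts for escalation and, if SAP 5.1 is applied literally, not for the primary endpoint.

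With six patients, one event decides whether a dose qualifies as the MTD. Which count applies should be fixed before the data are seen.

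Two related gaps sit beside this. The next dose level may open once 42 days have passed, although a patient in the current cohort may still be receiving make-up fractions and still be under DLT assessment. And no dose is stated for radiotherapy days after Day 42, so in a 20 mg or 30 mg cohort it is unclear whether an overrun DLT arose on the cohort dose or on the 40 mg maintenance dose.

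**Working it through.** **Inputs from the documents.** 30 fractions of 2 Gy, Monday to Friday (Protocol 4.2 and Appendix 10.6). MTD threshold of at most 1 of 6 (Protocol 5.2.4): 1/6 = 16.7%, which reproduces the stated 17%.

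**Assumptions, not from the documents.** A 42-day DLT risk p of 0.10 to 0.30, a constant daily hazard, independent patients, and missed fractions made up on the next weekdays at the end of the course.

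**Step 1: when the windows separate.** Day of the last fraction, counting weekdays from each possible start day:

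| Fractions missed | Last RT day |
|---|---|
| 0 | 40 (Monday start) or 42 |
| 1 | 43 for every start day |
| 2 | 44, or 46 (Friday start) |
| 5 | 47 (Monday start) or 49 |

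With nothing missed the two windows capture the same radiotherapy days. One missed fraction is enough to separate them.

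**Step 2: what one event does.** One DLT by Day 42 plus one in the overrun gives 2/6 = 33% to the end of 60 Gy (the dose fails), and 1/6 = 17% to Day 42 (the dose qualifies).

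**Step 3: risk in the overrun.** For a patient without DLT at Day 42 and an overrun of d days, q = 1 − (1 − p)^(d/42). For d = 1, q is 0.25% (p = 0.10) to 0.85% (p = 0.30); for d = 7, 1.7% to 5.8%.

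**Step 4: chance that the counts disagree.** If k of six patients overrun, the probability of at most 1 DLT by Day 42 but at least 2 by the end of radiotherapy is

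p(1 − p)^5 × {k[1 − (1 − q)^(k−1)] + (6 − k)[1 − (1 − q)^k]} + (1 − p)^6 × P(at least 2 late DLTs among k).

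For k = 1 this reduces to 5p(1 − p)^5 q. With p = 0.10 and d = 1: 5 × 0.10 × 0.5905 × 0.0025 = 0.07%. With p = 0.30 and d = 7: 5 × 0.30 × 0.1681 × 0.0577 = 1.45%. For k = 6, p = 0.30 and d = 7: 0.3025 × 0.2571 + 0.1176 × 0.0428 = 8.28%.

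| Patients overrunning | Overrun | p = 0.10 | p = 0.20 | p = 0.30 |
|---|---|---|---|---|
| 1 of 6 | 1 day | 0.07% | 0.17% | 0.21% |
| 1 of 6 | 7 days | 0.51% | 1.20% | 1.45% |
| 3 of 6 | 1 day | 0.22% | 0.52% | 0.64% |
| 3 of 6 | 7 days | 1.57% | 3.59% | 4.28% |
| 6 of 6 | 1 day | 0.45% | 1.04% | 1.27% |
| 6 of 6 | 7 days | 3.21% | 7.15% | 8.28% |

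The calculation fixes the cohort at six. It does not model the whole 3+3 path, where a level with no DLT in three patients escalates at three.

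**The case against.** The best defence is that 42 days is only the nominal length of a six-week course. Several texts fit that reading. Protocol 5.2.4 sets aside only DLTs after maintenance has started, and maintenance follows radiotherapy. SAP 5.1 ties its period to drug given together with radiotherapy, which describes an overrun too. The separate listing in SAP 7.4 gives no day number. SAP Section 9, which SAP 7.4 cites for time to first occurrence, cannot be read in the public text and might define the period. On escalation, 42 days is a minimum, monitor agreement is required, and the overrun rule follows in the same section.

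Much of this stands. A reader might infer that 5.2.4 flatly contradicts 4.1.4.1.1; its boundary at the start of maintenance does not support that, and it can be read as agreeing. A reader might also infer that overrun DLTs would go unreported. They would not: the DLT tables in Protocol 7.3.1 state no 42-day limit, and SAP 7.8.1 plans a table of patients with investigator-defined DLTs.

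The defence does not remove the wording of SAP 5.1. No visible text calls the 42 days nominal or says which rule prevails. The authors could write an extension when they wanted one: the background in Protocol 1.2.2 has temozolomide continuing "throughout the 42 day concomitant period (up to 49 days". SAP 5.1 has nothing similar. Nor does a 42-day minimum say that the overrun window must have closed before the next level opens.

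**Conclusion.** The point holds as a conflict between two stated rules: the 60 Gy window in Protocol 4.1.4.1.1 and the literal 42-day period in SAP 5.1. Protocol 5.2.4 is ambiguous, not in conflict. The escalation timing and the dose on overrun days are open on the same calendar days.

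Severity is minor. It matters only for patients whose radiotherapy runs past Day 42. The chance that the two counts fall on opposite sides of the MTD threshold is 0.07% to 1.5% if one of six patients overruns by 1 to 7 days, and at most about 8% in the extreme case of all six overrunning by 7 days. These figures rest on the assumed 10% to 30% DLT risk and a constant hazard. The sample size is unaffected.

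**What to change.** - **SAP 5.1:** define the DLT window as first dose to the later of Day 42 and the last radiotherapy fraction. The separate listing in SAP 7.4 then starts after that window.
- **Protocol 5.2.4:** use the same wording. If 42 days was meant as a nominal label, this records it.
- **Protocol 4.1.4.1.1:** require every patient in the cohort to have completed that window before the next dose level opens.
- **Protocol 4.1.4.1:** state that patients stay on the cohort dose of BIBW 2992 until the last fraction, so that an overrun DLT is attributed to the right dose. Lengthening the window without this would leave attribution unclear in the 20 mg and 30 mg cohorts.

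The cost is wording in both documents and a few days' wait before escalation when radiotherapy overruns.
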